9.5.2.6 Immediate Reporting of Serious Adverse Events and Events of Special Interest

The Sponsor is required to inform worldwide regulatory authorities of SAEs and Ocular Events of Special Interest that meet specific criteria. Therefore, the Sponsor must be notified immediately regarding any SAE and Ocular Events of Special Interest that occur after informed consent is obtained.

The following serious and non-serious adverse events (ie, Ocular Events of Special Interest) require a 15-day alert report:

- cataract, lens, or lenticular abnormality or change, opacity, opacification or opalescence
- blindness, night blindness, visual acuity or vision decrease, abnormality or change, visual acuity test abnormality or change
- retinal, macular, or optic nerve degeneration, abnormality or change; retinal pigment epithelium detachment, abnormality or change
- color vision decrease, abnormality or change

Within 24 hours of learning of any AE that meets one of the criteria for an SAE, the study site personnel must report the event to the Sponsor's Global Drug Safety department on the SAE Form for Clinical Trials.

Within 24 hours of learning of any non-serious Ocular Event of Special Interest, the study site personnel must report the event on the Ocular Event Reporting Form. Serious Ocular Events should be reported on the SAE Form for Clinical Trials.

In addition to completing the appropriate form, the Sponsor's Study Safety Physician may also be notified by telephone.

If, during follow-up, any nonserious AE worsens and eventually meets the criteria for an SAE, that AE should be recorded as a new SAE.

The site must transmit the SAE Form for Clinical Trials or the Ocular Event of Special Interest form to the SAE fax number shown below. Even if an initial report is made by telephone, the SAE Form for Clinical Trials or the Ocular Event of Special Interest form, completed with all available details, must still be faxed within 24 hours of knowledge of the event at the study site.

Supplemental information should be submitted as soon as available and may include laboratory results, radiology reports, progress notes, hospital admission and emergency room notes, holding and observation notes, discharge summaries, autopsy reports, and death certificates.

The Investigator is expected to take all therapeutic measures necessary for resolution of the SAE. Any medications or procedures necessary for treatment of the SAE must be recorded on the appropriate pages of the patient's eCRF. All SAEs and Ocular Events of Special Interest are to be followed by the study staff until resolution or until the SAE or Ocular Event of Special Interest is deemed stable. *The Sponsor may contact the study site to solicit additional information or follow up on the event.*

Fax the SAE Form for Clinical Trials to the Sponsor:

SAE Form fax number:

[figure not shown]
The Medical Emergency Phone number is provided in Regulatory Binder contact list.

[figure not shown]
9.5.2.7 Reporting of Pregnancies Occurring During the Study

[figure not shown]
Study site personnel must report every pregnancy from the time the patient signs the ICF until 30 days after the last dose of investigational product. Within 24 hours of learning of the pregnancy, the study site personnel must report the event to the Sponsor's Global Drug Safety department on the Clinical Trial Pregnancy Form and fax it to the SAE/Pregnancy fax number stated in Section 9.5.2.6, even if no AE has occurred. Pregnancies in female partners of male patients occurring during the time frame described above must also be reported.

The pregnancy must be followed to term and the outcome reported by completing a follow-up a Clinical Trial Pregnancy Form. If the pregnancy is associated with an SAE (e.g., if the mother is hospitalized for hemorrhage), a separate SAE Form for Clinical Trials must be filed as described in Section 9.5.2.6 with the appropriate serious criterion (e.g., hospitalization) indicated in addition to the Pregnancy Form.

9.5.3 Investigational Product Concentration Measurements

Blood samples will be collected by a qualified phlebotomist via venipuncture using lavender-top Vacutainer tubes containing potassium K₂EDTA as the anticoagulant. A 2-mL tube will be used to collect the samples for determination of the plasma concentrations of cariprazine and its metabolites.

Four blood samples (2 mL each) will be collected at Visit 4 (Week 2), Visit 5 (Week 4), Visit 6/ET (Week 6), and Visit 7 (Week 7). Samples may be collected at any time during the visit. The date and time of plasma sampling will be recorded in the eCRF along with the date and approximate time of the previous 3 doses of investigational product. Every effort should be made to collect PK samples for each patient. However, if for reasons of safety or patient refusal, blood sampling is not possible, the PK sample can be skipped.

All Vacutainer and plasma collection tubes must be prechilled in an ice bath before use.

The clock times of all blood draws will be recorded for each patient. All Vacutainer and polypropylene tubes will be labeled at the study center with a code number that corresponds to the PID number, visit number, date, and blood draw time. The central laboratory will supply the labels with code numbers, blood Vacutainer tubes, and the polypropylene tubes. Other laboratory supplies are the responsibility of the Investigator.

Samples must be centrifuged for plasma harvesting within 30 minutes of blood draw.

For details on blood sample collection, plasma separation, storage, and shipment, see the instructions from the central laboratory (Central Laboratory Manual).

[figure not shown]
9.5.4 Health Economic and Outcomes Research Assessments

[figure not shown]
Not applicable.

[figure not shown]
9.5.5 Schedule of Assessments

The schedule of study procedures and assessments is tabulated by visit in the Schedule of Evaluations in Section 2.0. The descriptions of the procedures to be performed at each visit are provided below.

9.6 DATA QUALITY ASSURANCE

9.6.1 Data Monitoring

Before any patient enters the study, a Sponsor representative will meet with the Investigator and the study site staff to review the procedures to be followed during the study. Electronic data capture (EDC) functionality training is provided via computer-based training to train Investigators and authorized designees on recording the data in the eCRFs using the EDC system. After the first patient is enrolled, the Sponsor representative, a Regional Site Manager (RSM) or designee, will periodically monitor the progress of the study by conducting on-site visits. This RSM or designee will review query statuses remotely, possibly warranting more frequent communication and/or site visits with the Investigator and the study site staff. The Investigator will make available to the RSM or designee source documents (written notes and electronic medical records, if used), signed consent forms, and all other study-related documents. The Investigator and the study site staff will be responsible for data entry of patient data into the eCRFs via the EDC system, resolving data queries generated via the EDC system and providing missing or corrected data. The Investigator or designee will be responsible for approving all changes performed on the data, and endorsing the patient data within the EDC system. This approval method will include applying an electronic signature linked to a uniquely assigned username and password that together will represent a traditional handwritten signature used in the past.

9.6.2 Data Recording and Documentation

Data collection will involve the use of the Sponsor's EDC system, to which only authorized personnel will have access. Patient's data are to be entered into the EDC system by the Investigator or designee using their assigned EDC user account. After data entry into the EDC system by the Investigator or designee, a combination of manual and programmatic edit checks will be used to review the data for completeness, logic, and adherence to study protocol. As a result of these edits checks, data monitoring and reviews; queries may be electronically issued to the site and should be answered electronically via the EDC system.

Each query will carry identifying information (assigned username, date and time) to assist the Sponsor and the Investigator on the origin of the data clarification request and the response provided by the Investigator. All data changes made to the patient's data via a data query will be approved by the Investigator prior to final database lock.

After all data have been reviewed and all issues have been resolved, the database will be locked.

All data collected in the context of this study will be stored and evaluated per regulatory requirements and applicable guidance for electronic records. Also, data will be stored and evaluated in such a way as to guarantee patient confidentiality in accordance with the legal stipulations applying to confidentiality of data. Study records (e.g., copies of eCRFs, laboratory reports, patient diaries, regulatory documents, etc.) will be retained at the site, along with adequate source documentation, according to FDA and ICH requirements. All study records must be available for inspection by the Sponsor, its authorized representatives, and the FDA or other health authorities.

9.7 STATISTICAL METHODS AND DETERMINATION OF SAMPLE SIZE

9.7.1 Patient Populations

Four populations will be considered in the statistical analysis of the study.

9.7.1.1 Screened Population

The Screened Population will consist of all patients who signed informed consent and received a PID number.

9.7.1.2 Randomized Population

The Randomized Population will consist of all patients in the Screened Population who were randomized to a treatment group in the study.

9.7.1.3 Safety Population

The Safety Population will consist of all patients in the Randomized Population who took at least 1 dose of double-blind investigational product.

9.7.1.4 Intent-to-Treat Population

The Intent-to-Treat (ITT) Population will consist of all patients in the Safety Population who had at least 1 postbaseline assessment of MADRS total score.

9.7.2 Patient Disposition

The number and percentage of patients in 3 of the study populations (Randomized, Safety, and ITT) will be summarized by treatment group and study center; the Screened Population will be summarized overall only by study center.

Screen-failure patients (ie, patients screened but not randomized) and the associated reasons for failure to randomize will be tabulated overall for the Screened Population. The number and percentage of patients who completed the double-blind treatment period, and of patients who prematurely discontinued during the same period and who entered the safety follow-up period will be presented for each treatment group and pooled across treatment groups for the Randomized Population. Patients are considered to have entered the safety follow-up period if they had Visit 7 (Week 7). The reasons for premature discontinuation from the double-blind treatment period as recorded on the termination pages of the eCRFs will be summarized (number and percentage) by treatment group for the Randomized Population.

9.7.3 Demographics and Other Baseline Characteristics

Demographic parameters (e.g., age, race, ethnicity, sex, weight, height, BMI) and other baseline characteristics will be summarized by treatment group for the Safety and ITT populations.

Prior medication is defined as any medication taken before the date of the first dose of double-blind investigational product. *Concomitant medication* is defined as any medication taken on or after the date of the first dose of double-blind investigational product.

Both prior and concomitant medication use will be summarized by the number and proportion of patients in each treatment group receiving each medication within each therapeutic class for the Safety Population. Multiple medication use by a patient will only be counted once.

9.7.4 Extent of Exposure and Treatment Compliance

9.7.4.1 Extent of Exposure

Exposure to double-blind investigational product for the Safety Population during the double-blind treatment period will be summarized for treatment duration, calculated as the number of days from the date of the first dose of double-blind investigational product taken to the date of the last dose taken, inclusive. Descriptive statistics (n, mean, standard deviation, minimum, median, and maximum) will be presented by treatment group.

9.7.4.2 Measurement of Treatment Compliance

Dosing compliance for a specified period is defined as the total number of capsules actually taken by a patient during that period divided by the number of capsules that were expected to be taken during the same period multiplied by 100. The total number of capsules actually taken during a specific period is calculated as the number of days in that period multiplied by the number of capsules taken each day during that period. The number of capsules expected to be taken for a specific treatment period will be calculated by multiplying the number of days in that period by the number of capsules to be taken per day. Descriptive statistics for investigational product compliance will be presented by treatment group for each period between 2 consecutive visits, as well as for the whole double-blind treatment period of the study for the Safety Population.

9.7.5 Efficacy Analyses

All efficacy analyses will be based on the ITT Population, unless stated otherwise. The baseline for each specific efficacy endpoint is defined as the value recorded at Visit 2/Week 0. If this value is not available, the last available value before the first dose of double-blind investigational product will be used as the baseline value. Efficacy results will be considered to be statistically significant after consideration of the multiplicity-control strategy for controlling the Type I error at 0.05 level; details are described in Section 9.7.5.2. Nominal p-values may be computed for other efficacy analyses as a measure of strength of association between the endpoint and the treatment effect rather than formal tests of hypotheses. All statistical hypothesis tests will be performed at the 2-sided 5% significance level for main effects. All confidence intervals will be 2-sided 95% confidence intervals, unless stated otherwise.

For efficacy analyses in which study center is a factor, a small center will be defined as a center with fewer than 2 patients in at least 1 treatment group in the ITT Population. Small centers will be pooled to form pseudo-centers so that each treatment group includes at least 2 ITT patients within the center. Pooling will be done within each country using the following algorithm:

Based on the number of ITT patients, small centers will be ordered from the largest to the smallest, and centers of the same size will be ordered from the largest center number to the smallest center number. The pooling process starts with the largest small center from the top, which will be pooled with the smallest from the bottom until a non-small center is formed. The process will be repeated using the small centers left out after the first pass. If any centers are left out at the end of the process, they will be pooled with the smallest pseudo-center. If there is more than 1 smallest pseudo-center, the pseudo-center with the smallest center number will be selected. In case that the pseudo center formed by pooling all small centers is still a small center, it will be pooled with the smallest non-small center. If there is more than 1 smallest non-small center, the one with the smallest center number will be selected.

These pseudo-centers will be used for all efficacy analyses when the model is adjusted for study center.

9.7.5.1 Primary Efficacy Parameters

The primary efficacy parameter will be the change from baseline to Week 6 in MADRS total score. The primary analysis will be performed using a MMRM with treatment group, study center, visit, and treatment group—by-visit interaction as fixed effects and the baseline value and baseline by-visit interaction as covariates. An unstructured covariance matrix will be used to model the covariance of within-patient scores. The Kenward-Roger approximation will be used to estimate denominator degrees of freedom. The analysis will be performed based on all postbaseline scores using only the observed cases without imputation of missing values.

[figure not shown]

9.7.5.2 Secondary Efficacy Parameters

The secondary efficacy parameter will be change from baseline to Week 6 in CGI-S score. The secondary efficacy parameter will be analyzed using an MMRM with treatment group, study center, visit, and treatment group—by-visit interaction as fixed effects and the baseline CGI-S score and baseline CGI-S score—by-visit interaction as the covariates. An unstructured covariance matrix will be used to model the covariance of within-patient scores. The Kenward-Roger approximation will be used to estimate denominator degrees of freedom.

To control the overall type I error rate for multiple comparisons of 2 active doses versus placebo at Week 6 for the primary and secondary efficacy parameters, the parallel gatekeeping procedure will be implemented (Chen et al, 2005). The 4 null hypotheses will be grouped into 2 families denoted by F1 and F2, with F1 consisting of 2 null hypotheses for comparisons of the 2 active doses versus placebo in change from baseline to Week 6 in MADRS total score, and F2 consisting of 2 null hypotheses for comparisons of the 2 active doses versus placebo in change from baseline to Week 6 in CGI-S score. Family F1 will serve as the parallel gatekeeper for F2. The matched gatekeeping procedure utilizes the special logical relationship between the primary and the secondary parameters to enhance the power of statistical testing. The secondary efficacy parameter will be tested at a specific dose only if the corresponding primary efficacy parameter is statistically significant. The Simes test will be used to derive the local p-values for the interaction hypotheses. The adjusted p-values for the 4 elementary hypotheses will be calculated based on the closed testing principle. Statistical significance will be determined by comparing the adjusted p-values to $\alpha = 0.050$.

9.7.6.6 Investigational Product Plasma Concentration Parameters

Plasma samples will be analyzed for the concentrations of cariprazine and its desmethyl and didesmethyl metabolites using a validated bioanalytical method. A population PK approach will be used to estimate individual-level drug-exposure parameters (i.e., steady-state area-under-the-curve (AUC), steady-state maximum concentration [Cmax], steady-state minimum concentration [Cmin]) for each of the 3 analytes. This will be performed via the use of appropriate nonlinear mixed-effects modeling software. The effects of demographics/covariates (eg, gender, body weight, height, concomitant medications) on the pharmacokinetics of the 3 analytes will be evaluated. The relationship, if any, between effectiveness and drug-exposure parameters will be explored.

9.7.7 Health Economics and Outcomes Research Analyses

Not applicable.

9.7.8 Interim Analysis

No interim analysis is planned for this study.

9.7.9 Determination of Sample Size

The primary efficacy endpoint is the change from baseline at Week 6 in MADRS total score. The secondary endpoint is the change from baseline at Week 6 in CGI-S score. For the comparison of the primary endpoint, the sample size of 160 subjects per arm will provide approximately 82% statistical power to show statistically significantly higher effect in each dose of cariprazine versus placebo. The study has statistical power of 90% to show at least one of the two cariprazine doses is statistically significantly more efficacious than placebo in the primary endpoint. These calculations assumed an effect size of 0.36 (treatment group difference relative to SD). For a given successful (statistically significant) dose versus placebo with respect to the primary endpoint, its probability in detecting an effect size of 0.36 as statistically significant versus placebo with respect to the secondary endpoint is 88%. All statistical powers presented in this section were calculated adjusting for multiple comparisons using matched parallel gatekeeping procedure with the family-wise Type I error rate being controlled at a 0.05 level (2-sided). The dropout rate is assumed to be 22% at Week 6. Within-person correlation for both primary and secondary endpoints is assumed to be 0.6, as well as correlation between the two endpoints (primary and secondary) to be 0.6. Assumptions of effect sizes, correlation coefficients, and drop-out rate are based on RGH-MD-56 study.

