Study RGH-MD-56 was 11 weeks in duration and comprised up to 14 days of screening followed by 8 weeks of double-blind treatment and 1 week of safety follow-up. A total of 584 bipolar I patients were randomized to 1 of 4 treatment groups and 578 patients received at least 1 dose of the investigational product: placebo (n = 145), cariprazine 0.75 mg/day (n = 141), cariprazine 1.5 mg/day (n = 146), cariprazine 3 mg/day (n = 146). Overall, 72.5% of the patients completed the study: 72.4% in the placebo group, 73.0% in the cariprazine 0.75 mg/day group, 80.1% in the cariprazine 1.5 mg/day group, and 64.4% in the cariprazine 3 mg/day group. The average patient age was 42 years, and approximately 62% were female. For both the primary and secondary efficacy parameters, change from baseline in MADRS total score and Clinical Global Impressions-Severity (CGI-S) score at Week 6, statistically significant improvement was demonstrated for the cariprazine 1.5 mg dose relative to placebo. Nominally significant improvement was shown for cariprazine 3 mg, which did not remain statistically significant after adjusting for multiplicity. No statistically significant treatment effect was shown for the 0.75 mg dose at Week 6. A post-hoc analysis of patients who completed the full 8 weeks of treatment (completer population) in Study RGH-MD-56 demonstrated similar reductions from baseline relative to placebo in MADRS total score for the cariprazine 1.5 and 3 mg/day groups at Week 6 and Week 8. Cariprazine was generally well-tolerated. No deaths were reported during the study. Serious adverse events were reported for 5 patients (3.4%) in the placebo group, 1 patient (0.7%) in the cariprazine 0.75 mg group, and 2 patients (1.4%) each in the cariprazine 1.5 mg and 3 mg treatment groups. Adverse events that led to discontinuation were reported in similar proportions of patients across the placebo (10.3%) and cariprazine (8.2%-11.6%) treatment groups. The most common AEs that led to discontinuation were akathisia, agitation, anxiety, and depression. Overall, TEAEs were reported for 55% of patients in the placebo treatment group and 57%-62% of patients in the cariprazine treatment groups. Akathisia and irritability were the only TEAEs reported for $\geq 5\%$ of patients in any cariprazine treatment group and at an incidence at least twice that of the placebo group.

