9.4.4 Selection of Dosages in the Study

The doses of cariprazine selected for this study were based on the results from 2 completed studies in patients with bipolar depression (RGH-MD-52 and RGH-MD-56), as well as experience in the cariprazine development program in healthy volunteers and patients with other indications and other atypical antipsychotics for the treatment of bipolar depression. Study RGH-MD-52 indicated numerically better results for the high-dose cariprazine group (1.5-3.0 mg/day) relative to placebo up to end of Week 6. In the cariprazine low-dose group (0.25-0.75 mg/day), better efficacy was observed following a dose increase, and tolerability was not compromised. Thus, cariprazine 0.75, 1.5, and 3.0 mg/day were selected for further evaluation in Study RGH-MD-56.

In Study RGH-MD-56, for both the primary and secondary efficacy parameters, change from baseline in MADRS total score and CGI-S score at Week 6, statistically significant improvement was demonstrated for the cariprazine 1.5 mg dose relative to placebo. Nominally significant improvement was shown for cariprazine 3 mg, which did not remain statistically significant after adjusting for multiplicity. No statistically significant treatment effect was shown for the 0.75 mg dose at Week 6. A post-hoc analysis of patients who completed the full 8 weeks of treatment (completer population) in Study RGH-MD-56 demonstrated similar reductions from baseline relative to placebo in MADRS total score for the cariprazine 1.5 and 3 mg/day groups at Week 6 and Week 8.

The primary efficacy results and the post-hoc completers analysis in Study RGH-MD-56 led to the selection of the cariprazine 1.5 and 3 mg/day doses for further evaluation in this study. A dose higher than 3 mg/day was not chosen because of concerns related to the potential for higher extrapyramidal symptom rates with increasing cariprazine dose.

A fixed-dose regimen allows for unambiguous evaluation of safety and efficacy of individual doses

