5.1.2 Determination of Sample Size

The primary efficacy endpoint is the change from baseline at Week 6 in MADRS total score. The secondary endpoint is the change from baseline at Week 6 in CGI-S score. For the comparison of

the primary endpoint, the sample size of 160 subjects per arm will provide approximately 82% statistical power to show statistically significantly higher effect in each dose of cariprazine versus placebo. The study has statistical power of 90% to show at least one of the two cariprazine doses is statistically significantly more efficacious than placebo in the primary endpoint. These calculations assumed an effect size of 0.36 (treatment group difference relative to SD). For a given successful (statistically significant) dose versus placebo with respect to the primary endpoint, its probability in detecting an effect size of 0.36 as statistically significant versus placebo with respect to the secondary endpoint is 88%. All statistical powers presented in this section were calculated adjusting for multiple comparisons using matched parallel gatekeeping procedure with the family-wise Type I error rate being controlled at a 0.05 level (2-sided). The dropout rate is assumed to be 22% at Week 6. Within-person correlation for both primary and secondary endpoints is assumed to be 0.6, as well as correlation between the two endpoints (primary and secondary) to be 0.6. Assumptions of effect sizes, correlation coefficients, and drop-out rate are based on RGH-MD-56 study.

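### Does the outcome of RGH-MD-56 undercut the 0.36 effect size behind the 82% power stated for the 3.0 mg dose?

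*Protocol*

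**What the plan says.** Protocol 9.7.9 and SAP 5.1.2 carry the same sample-size text. With 160 patients per arm, the primary comparison "will provide approximately 82% statistical power to show statistically significantly higher effect in each dose of cariprazine versus placebo". Power for at least one dose is put at 90%. The chance of also winning on CGI-S, for a dose that has won on MADRS, is put at 88%. All three rest on one standardised effect: "These calculations assumed an effect size of 0.36 (treatment group difference relative to SD". The other inputs are 22% dropout at Week 6, a within-person correlation of 0.6, a between-endpoint correlation of 0.6, and the matched parallel gatekeeping procedure at a two-sided family-wise 0.05. On where these come from: "Assumptions of effect sizes, correlation coefficients, and drop-out rate are based on RGH-MD-56 study".

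Protocol 7.0 describes that study. In it, "statistically significant improvement was demonstrated for the cariprazine 1.5 mg dose relative to placebo". For the other dose: "Nominally significant improvement was shown for cariprazine 3 mg, which did not remain statistically significant after adjusting for multiplicity". Protocol 9.4.4 gives the reason for taking both doses forward: "The primary efficacy results and the post-hoc completers analysis in Study RGH-MD-56 led to the selection of the cariprazine 1.5 and 3 mg/day doses". The completer analysis is said to have shown "similar reductions from baseline relative to placebo in MADRS total score for the cariprazine 1.5 and 3 mg/day groups".

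**The concern.** The two doses are separate confirmatory comparisons, and the source study did not treat them alike: one passed its multiplicity-adjusted test and the other did not. Yet both receive the same effect size, attributed to that study, and the same 82%. Had 3 mg shown 0.36 in RGH-MD-56, with 146 patients against 145 on placebo, its p-value would have been small enough to pass a usual three-dose correction. So 0.36 looks too high for 3 mg.

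At stake is how a result for 3.0 mg is read. If that comparison misses, a reader may believe it had an 82% chance when the earlier evidence pointed lower, and may count the miss too heavily against the dose. The completer analysis does little to close the gap. It is post hoc, reported without figures, and conditions on finishing 8 weeks, which only "64.4% in the cariprazine 3 mg/day group" did, against 80.1% on 1.5 mg.

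**Working it through.** **1. Reproducing the stated power.** Inputs from Protocol 9.7.9: N = 160 per arm, d = 0.36, 22% dropout at Week 6, within-person correlation 0.6. Visits at Weeks 1, 2, 4 and 6 are from SAP Table 5-13. Assumed: dropout linear in time, compound symmetry.

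- Information for the visit means is the sum over dropout patterns of (pattern fraction × inverse covariance of the visits observed). Effective n is N divided by the Week 6 diagonal element of the inverse of that sum: 136.6 per arm.
- Non-centrality = 0.36 × √(136.6/2) = 2.98.
- The 15 intersection tests were simulated with the SAP 5.1.1.3.2 weights and Simes (2 million draws, correlation 0.5 between doses through the shared placebo arm, 0.6 between endpoints). Results: 81.8% per dose, 90.0% for at least one, 89.1% for CGI-S given a MADRS win. The plan states 82%, 90% and 88%.

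**2. What the RGH-MD-56 account implies for 3 mg.** Arm sizes (146 and 145) and 8-week completion (64.4% and 72.4%) are from Protocol 7.0. The standard error of d is √(1/n₁ + 1/n₂) on three bases:

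- no data loss: √(1/146 + 1/145) = 0.117;
- MMRM, taking Week 6 dropout as 6/8 of 8-week dropout (26.7% and 20.7%) and correlation 0.6: effective n 119.7 and 125.1, giving 0.128;
- completers only: 0.644 × 146 = 94.0 and 0.724 × 145 = 105.0, giving 0.142.

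An observed 0.36 would give p = 0.002, 0.005 and 0.011 respectively. The d that just reaches a given p is z(p) × SE. Nominal significance sets the lower end at p = 0.05. The upper end depends on the unstated adjustment: 0.05/3 = 0.0167 for Bonferroni over three doses, or 0.05/6 = 0.0083 if six tests shared the alpha.

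| Basis | p if d = 0.36 | d at p = 0.05 | d at p = 0.0167 | d at p = 0.0083 |
|---|---|---|---|---|
| No loss | 0.002 | 0.230 | 0.281 | 0.309 |
| MMRM | 0.005 | 0.251 | 0.306 | 0.338 |
| Completers | 0.011 | 0.278 | 0.340 | 0.375 |

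**3. Power for 3.0 mg in this trial at those effects.** Same simulation, 1.5 mg held at 0.36:

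| Basis | p from 0.05 to 0.0167 | at p = 0.0083 |
|---|---|---|
| No loss | 46% to 62% | not run |
| MMRM | 52% to 69% | 77% |
| Completers | 61% to 77% | 85% |

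A larger effect for 1.5 mg raises these by about 2 to 3 points; with 0.47 there, the top of the completers range up to 0.0167 is about 80%.

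**4. How firmly this excludes 0.36.**

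- The 95% upper limit for the true 3 mg effect on the MMRM basis runs from 0.251 + 1.96 × 0.128 = 0.50 to 0.306 + 1.96 × 0.128 = 0.56. The true effect could well be 0.36.
- Completers only with a threshold of 0.0083 allows an observed 0.375, above 0.36.
- A fixed sequence from 1.5 mg to 0.75 mg to 3 mg would have stopped 3 mg at any p-value, because 0.75 mg failed. A sequence starting at 3 mg or at 0.75 mg is ruled out, since 1.5 mg was declared significant.
- Illustrative effects of 0.42 for 1.5 mg and 0.30 for 3 mg average (0.42 + 0.30)/2 = 0.36. With a standard error of about 0.125 for the dose contrast, z = 0.12/0.125 = 0.96, so such a pair would not show that the doses differ. At those values power for at least one dose is 92%, above the stated 90%.

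**The case for a change.** The strongest case for a change is that the plan does more than condition on 0.36: it says the value comes from a study in which, on its own account, the two doses had different outcomes. Under Bonferroni, Holm or Hochberg over three doses, an observed 0.36 for 3 mg would have stayed significant on every data-loss basis in the table, and even the 0.0083 threshold on the MMRM basis gives 77%, short of 82%. The sponsor holds the estimates, so giving power by dose would cost one program run and a few sentences.

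Part of this stands. The arithmetic is right, an ordinary adjustment does point below 0.36, and the documents do not say which dose or pooling produced the figure. But the 0.25 to 0.31 is back-calculated, not reported. It depends on an adjustment rule, a dropout pattern and a correlation structure that the documents do not give for RGH-MD-56. An assumption based on a study need not equal the estimate for each arm: a common value across two doses with overlapping uncertainty is an ordinary planning choice. Powering each dose at its own point estimate has its own weakness, because the estimate for a dose picked out by its significance tends to be too high.

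**Conclusion.** No change to the plan is needed. The 82%, 90% and 88% follow from their stated inputs to within about one percentage point, and both documents present them as conditional on 0.36. If RGH-MD-56 used an ordinary three-dose adjustment, its 3 mg estimate was below 0.36: about 0.25 to 0.31 on an MMRM basis and 0.23 to 0.34 across data-loss assumptions. That corresponds to 3.0 mg power of about 46% to 77% with 1.5 mg at 0.36, or up to about 80% with a larger 1.5 mg effect. Under a stricter or fixed-sequence rule an estimate of 0.36 or more is possible, with 85% power at 0.375. The documents cannot decide between these cases, so they do not show the stated figure to be wrong.

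What remains is missing detail on whether 0.36 is a single-dose estimate, a pooled value or a target. A sentence on its source and a short table of power by effect size would help a reader, but they are optional. Sample size, alpha, the MMRM and the gatekeeping procedure would stay as they are, and so would the trial's result.
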